6.3 Study Completion

6.3.1 Study Completion

For purposes of the Investigator notifying the IRB, the study is complete when all subjects at the site have been exited. Sponsor approval is required prior to IRB notification.

6.3.2 Early Study Termination/Suspension

If during the study it becomes evident to the Sponsor that the study should be stopped prematurely or placed on hold, the study will be terminated and appropriate notification will be given to the Investigator(s), IRBs, and FDA, as applicable. Bausch + Lomb will instruct the Investigators to stop/restart dispensing study materials and will arrange for study closeout, if applicable, at each site.

6.4 Concomitant Medications/Therapy

Other ocular solutions, medications or drops are not allowed to be used by subjects during the study. Use of other contact lenses are not allowed.

Ocular medications, systemic or topical medications that, in the Investigator's opinion, could potentially affect ocular physiology or lens performance are also prohibited, unless medically necessary during the course of the study. If used during the course of the study, these medications must be recorded in the source document and the appropriate eCRF.

6.5 Treatment Compliance

The Investigator or other designee will review instructions and warnings for lens wear, lens care, handling, cleaning, and disinfecting with the subject. Any subject who does not follow instructions to a degree that, in the Sponsor or Investigator's opinion, jeopardizes the subject's well-being or the validity of the study, must be discontinued.

6.6 Protocol Deviations

The date of and reason for deviations (failure to comply with the protocol, eligibility or randomization errors, not done visits, out of window study visits, worn lenses not returned, habitual lenses not worn daily, etc.) will be documented in all cases. Significant or major protocol deviations impacting the safety of the subject or the integrity of the study must be reported by the Investigator to the IRB and Medical Monitor immediately. Reporting of all other protocol deviations must adhere to the requirements of the governing IRB.

A subject may continue to participate until the end of the study, unless the protocol deviations put the subject at risk, the subject's condition requires that the subject be discontinued from the study or other sections of this protocol state that the subject must be discontinued due to the deviation (see Section 3.2.3).

7.0 ADVERSE EVENTS

7.1 Adverse Event Definitions

For the purposes of this study, reportable adverse events (AEs) include ocular AEs and non-ocular serious adverse events (SAEs). All AEs will be classified first for seriousness and significance and then as to whether or not they are an adverse device effect (ADE), an anticipated serious adverse device effect (ASADEs) or an unanticipated serious adverse device effect (USADEs). AEs, ADEs, ASADEs, USADEs, SAEs, Significant Non-Serious AEs and Non-Significant Non-Serious AEs are defined as follows:

7.1.1 Adverse Event (AE)

Any untoward medical occurrence, unintended disease or injury, or untoward clinical signs (including abnormal laboratory findings) in a subject, user, or other persons, whether or not related to the investigational medical device. This definition includes events not related to the investigational medical device, comparator, or the procedures involved. For users or other persons, this definition is restricted to events not related to investigational medical devices.

Throughout the course of this study all efforts will be made to remain alert to reportable AEs. If an AE occurs the first concern will be the safety of the subject and appropriate medical intervention will be made.

AEs should be first assessed for seriousness and significance and then differentiated for device related and non-device related.

All reportable AEs occurring after signing of informed consent and through the subject's end of participation in the study must be reported. All reportable AEs must be followed until the event resolves or stabilizes.

Applicable AEs should be photo documented and communicated to the Medical Monitor in electronic form.

7.1.2 Adverse Device Effect (ADE)

An adverse device effect is an AE that is assessed to be related to the use of an investigational medical device. This definition includes AEs resulting from insufficient or inadequate instructions for use; deployment, implantation, installation, or operation; or any malfunction of the investigational medical device. This definition also includes any event resulting from use error or from intentional misuse of the investigational medical device.

7.1.2.1 Anticipated Serious Adverse Device Effect (ASADE)

An anticipated serious adverse device effect (ASADE) is an ADE that first meets the serious criteria (see Section 7.1.3) or significant non-serious criteria (see Section 7.1.4) and which, by its nature, incidence, severity or outcome, has been previously identified in the investigational plan or application (including a supplementary plan or application) and/or in the risk analysis report. ASADEs include:

- Corneal Ulcer (infectious or non-infectious)
- Keratitis
- Sensitivity to light (photophobia)
- Excessive eye secretions including mucopurulent discharge

- Blurred vision, rainbows or halos around objects
- Poor visual acuity (reduced sharpness of vision)
- Moderate to severe eye pain not relieved by removing the lens

7.1.2.2 Unanticipated Serious Adverse Device Effect (USADE)

An unanticipated serious adverse device effect (USADE) is an ADE that first meets the serious criteria (see Section 7.1.3) or significant non-serious criteria (see Section 7.1.4) and has an effect on health or safety or any life-threatening problem or death caused by, or associated with, a device if that effect, problem or death was not previously identified in nature, severity or degree of incidence in the investigational plan or application (including a supplementary plan or application), or any other unanticipated serious problem associated with a device that relates to the rights, safety, or welfare of subjects.

7.1.3 Serious Adverse Event (SAE)

An AE that:

- Led to death;
- Led to serious deterioration in the health of the subject, that resulted in:
 - A life-threatening illness or injury; or
 - A permanent impairment of a body structure or a body function (e.g., blindness); or
 - Inpatient or prolonged hospitalization; or
 - Medical or surgical intervention to prevent life-threatening illness or injury or permanent impairment to a body structure or a body function;
- Led to fetal distress, fetal death, or a congenital abnormality or birth defect.

Note: A planned hospitalization for a pre-existing condition, or a procedure required by the protocol, without serious deterioration in health, is not considered an SAE.

Serious adverse events are also those events that result in, or have potential to cause, either permanent impairment of an ocular function or damage to an ocular structure and may necessitate medical or surgical intervention.

Serious adverse events may include any hazardous, sight-threatening conditions occurring after exposure to the test article, including the following:

- A presumed infectious ulcer (defined as a progressive erosion of the corneal tissue). For the purposes of reporting, this includes:
 - Central or para-central location;
 - Penetration of Bowman's membrane;
 - Infiltrate ≥ 2 mm diameter;
 - Associated with iritis;
 - Associated with any increase in intraocular pressure;
 - Culture positive for microorganisms;
 - Increasing size or severity at subsequent visits;

NOTE: Signs of a presumed infectious corneal ulcer may include irregular focal infiltrates, active lesions with raised edges, significant diffuse infiltration, anterior corneal to mid-stromal involvement, erosion with overlying staining, conjunctival and lid edema, anterior chamber reaction (iritis), and severe bulbar and limbal redness. Symptoms associated with a presumed infectious ulcer (microbial keratitis) may include pain of rapid onset, severe redness, purulent or mucopurulent discharge, tearing, and photophobia.

- Any central or paracentral (within 6 mm of cornea) corneal event that results in permanent opacification (such as corneal scar or vascularization);
- Any serious adverse ophthalmic events including hypopyon and/or hyphema;
- Any neovascularization within the central 6 mm of the cornea;
- Permanent loss of ≥ 2 lines of BSCVA;
- All cases of iritis.

7.1.4 Significant Non-Serious Adverse Events

A significant non-serious adverse event is an AE that does not meet the serious criteria, is considered significant by the Sponsor, and requires expedited reporting. These events include:

- Peripheral non-progressive non-infectious corneal ulcers;
- All symptomatic corneal infiltrative events;
- All cases of corneal staining greater than or equal to Grade 3;
- A temporary loss of two or more lines of BSCVA (for greater than or equal to 2 weeks);
- Neovascularization cases Grade 2 or greater;
- Any ocular event that necessitates temporary lens discontinuation of greater than or equal to 2 weeks.

7.1.5 Non-Significant Non-Serious Adverse Events

A non-significant non-serious adverse event may include but are not limited to the following and does not require expedited reporting:

- Bacterial Conjunctivitis;
- Viral Conjunctivitis;
- Allergic Conjunctivitis;
- Corneal Edema;
- Contact Lens Related Papillary Conjunctivitis; and,
- Loss of Contrast Sensitivity

7.2 Adverse Event Treatment and Culturing

With any AE, treat the subject as appropriate to prevent further complications and to potentially resolve the event consistent with the standard of care.

For purposes of this study, the Sponsor requests that cultures should be obtained in cases of corneal ulcer or suspected ocular infection, unless medically contraindicated. Cultures should be taken from the cul-de-sac, lower eyelid margin, and the corneal lesion (if applicable). The required culturing techniques are outlined in Appendix B.

When a culture is obtained, the contact lenses and contact lens cases which were being utilized by the subject at the time of the AE should be collected from the subject for culturing and processing by the local clinical laboratory designated by the site.

Microbial data generated from returned subject supplies (e.g. lenses, lens cases, and/or lens case solutions) are for information only. Because microbes may be introduced into subject supplies during use, recovery of microbes from returned subject supplies cannot be presumed to indicate etiology or direction of organism transmission.

The ocular cultures, along with the associated contact lenses and contact lens cases, will be sent to the local clinical laboratory designated by the site for analysis. The clinical laboratory will report the culture results to the Investigator who will record the results in the eCRF.

7.3 Evaluations

When evaluating for reportable AEs, the Investigator must first determine if the event is serious (refer to Section 7.1.3 for criteria) and/or significant (refer to Sections 7.1.4 and 7.1.5) and then assess the severity of symptoms and the relationship of the event to the study device using the following guidelines:

7.3.1 Severity

- **Mild:** Subject awareness of a sign or symptom that is easily tolerated, requires no treatment, and does not interfere with subject's daily activities.
- **Moderate:** Subject awareness of a sign or symptom which may be a low level of concern to the subject and may interfere with daily activities but can be relieved by simple therapeutic care.
- **Severe:** A sign or symptom that interrupts the subject's daily activity and requires systemic therapy or other treatment

7.3.2 Relationship to Study Device and/or Rewetting Drops

[figure not shown]
- **Related:** There is at least a reasonable possibility that the AE is related to the study device (study solution) and/or rewetting drops. Reasonable possibility means that there is evidence to suggest a causal relationship or association between the study device and/or rewetting drops and the AE. Also referred to as an ADE.
- **Unrelated:** There is little or no reasonable possibility that the AE is related to the study device (study solution) and/or rewetting drops. This assessment implies that the AE has no evidence to suggest either a causal relationship

or association to the study device and/or Rewetting Drops and a more likely or certain alternative etiology exists.

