3.1 Description of Study Design

The study is designed to examine whether ABT12 Multi-Purpose Solution cleaning and disinfecting solution is non-inferior to COMPLETE Multi-Purpose Solution in several primary endpoints.

Approximately 252 subjects (504 eyes) will be enrolled in this three-month multicenter, randomized, masked, parallel, bilateral study at approximately 18 investigative sites in the United States (US). Approximately one-half of the subjects will be randomized to receive Bausch + Lomb investigational ABT12 Multi-Purpose Solution (Test), and approximately one-half of the subjects will be randomized to receive COMPLETE® Multi-Purpose Solution (Control). In addition, all subjects will be dispensed three new pairs (including two back-up pairs) of their habitual lenses at the beginning of the study for daily wear, and scheduled replacement lenses at the 1-Month and 2-Month Follow-up Visits.

All subjects will be seen for a Screening/Dispensing Visit, at which the informed consent form (ICF), including the Health Insurance Portability Accountability Act (HIPAA), will be obtained and eligibility will be assessed. If eligible, subjects will be dispensed three new pairs of their habitual lenses and a Study Kit containing a cleaning and disinfecting solution (sufficient for the entire study) according to the subject’s unique randomization schedule. Subjects may also be dispensed a supply of Sensitive Eyes® Rewetting Drops to be used on an as needed basis. Subjects must NOT use ANY other cleaning and disinfecting solution or rewetting drops during the study.

Subjects are to wear their study lenses on a daily wear basis, and are to use the Test or Control cleaning and disinfecting solution and care regimen after removing the lenses each day. Subjects will return their worn lenses to the unmasked designee at each monthly

follow-up visit, and will return their used and unused study solutions to the unmasked designee at the three month follow-up visit (or early study termination/suspension visit) for return to the Sponsor.

Eligible subjects will be enrolled into one of five lens groups based on their habitual contact lenses. Subjects will be randomized on a 1:1 basis within each lens group per site to receive either the Test or Control cleaning and disinfecting solution. The five lens groups will be comprised of habitual wearers of soft lenses based on lens material as indicated in the table below.

Table 1: Lens Groups

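### Section 7.3.2 labels an adverse event attributed only to the rewetting drops an adverse device effect, contrary to the definition in 7.1.2

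*Combined protocol and SAP*

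**What the plan says.** Four places in the protocol bear on causality.

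- **7.1.1** calls for a two-way split by device: "AEs should be first assessed for seriousness and significance and then differentiated for device related and non-device related".
- **7.1.2** gives the formal definition: "An adverse device effect is an AE that is assessed to be related to the use of an investigational medical device".
- **7.3** tells the investigator to "assess the severity of symptoms and the relationship of the event to the study device using the following guidelines".
- **7.3.2** holds those guidelines. It has two categories. Related applies when "There is at least a reasonable possibility that the AE is related to the study device (study solution) and/or rewetting drops", and the entry adds "Also referred to as an ADE". Unrelated applies when "There is little or no reasonable possibility that the AE is related to the study device (study solution) and/or rewetting drops", and it further requires that another cause be more likely or certain.

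The drops are an optional supply for either arm. Section 3.1 states: "Subjects may also be dispensed a supply of Sensitive Eyes® Rewetting Drops to be used on an as needed basis".

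Sections 7.1.2.1 and 7.1.2.2 define the ASADE and the USADE as kinds of ADE that meet the serious or the significant non-serious criteria. Section 7.4 requires USADEs to go to the reviewing IRB within 10 working days, or sooner if the IRB's own procedures say so.

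**The concern.** The term ADE is used in two senses. In 7.1.2 it means an effect of the investigational device. In 7.3.2 it means an effect of the solution, the drops, or both. The two serious classes and the USADE duty to the IRB are built on this term, so the wider sense carries into them.

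At stake is whether an ADE recorded in this trial can be read as attributed to the solution under study. Two investigators among roughly 18 sites could also class the same drops-only event differently, depending on which section they follow. An ADE recorded on the pooled scale does not show which product the investigator had in mind.

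**Working it through.** No arithmetic applies: the documents give no ADE count or rate. The check is to take one event through the text, namely an ocular event that the investigator attributes to the rewetting drops and not to the solution.

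1. **Are the drops part of the device?** Section 7.3.2 glosses study device as study solution and then names the drops as a second item, as its heading does. By the protocol's own wording the drops are separate from the study device, so they cannot be read into 7.1.2.
2. **Status under 7.1.2 and 7.3.** The event is not related to the study device. It is not an ADE, and under 7.1.1 it is non-device related.
3. **Rating under 7.3.2.** Related needs a reasonable possibility for either product, and the drops supply it. Unrelated needs little or no possibility for the same pair, so it is not available. The event must be rated Related.
4. **Label under 7.3.2.** Every Related event is an ADE, with no exception for drops-only attribution. This contradicts step 2.
5. **Carry-over.** If the event is serious or significant and of an identified kind, it now meets the ASADE wording. If it is not of an identified kind, it becomes a candidate USADE. The USADE text repeats a link to a device but does not say whether the drops count as one, so it does not reliably screen the event out.
6. **Reporting.** The 24-hour report to the Medical Monitor in 7.4 covers every serious and significant non-serious event whatever its cause, so it does not change. Only the USADE report to the IRB can change. Section 7.4 attaches no separate action to an ASADE.
7. **Does another section repair it?** No section asks for a rating by product. Drop use is recorded on the Symptoms/Complaints Form at each scheduled follow-up visit (6.1.2 to 6.1.4), but use is not a causality judgement. The AE form is not among the documents. It may collect the two attributions separately, but nothing in the protocol requires it.

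**Reach into the statistics.** The primary safety endpoint is slit lamp findings above Grade 2 (8.1.3). Section 8.6.1.5 classifies it from observed grades with no causality rating. Section 5.1 says AE rates carry no success criterion. Section 8 specifies no ADE table or test, and 8.6.1.1 leaves further detail to a separate statistical analysis plan.

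**The case against.** The best defence is that the pooling looks deliberate. The heading of 7.3.2 names both products, the drops are supplied under the protocol, and other drops are forbidden. The rule errs toward including too much: no solution-related event is missed, and any reporting error is an extra report. Widening 7.1.2 to match 7.3.2 would also remove the contradiction. All of this stands, and it limits the harm. But the protocol has not widened 7.1.2, and if it did, an ADE would still mix two products.

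The defence also notes that 7.1.2 speaks of an investigational device, while Section 1.0 describes the Control as currently marketed. Read literally, 7.1.2 would exclude effects of the Control solution too. That is correct, and the reconciliation has to settle it.

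Three stronger readings are tempting, and the documents do not support them.

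- **The Test/Control safety comparison is diluted.** No ADE comparison is specified, and the result would depend on the scale. Suppose, purely as an assumption, 4 Test and 2 Control solution-related events, plus 3 drops-only events per arm. The ratio moves from 4/2 = 2.0 to 7/5 = 1.4. With 1 to 6 drops-only events per arm it lies between 5/3 = 1.67 and 10/8 = 1.25. The difference in counts stays at 2 throughout. The one between-arm safety comparison the protocol does specify, for slit lamp findings, is a difference in proportions.
- **The attribution is lost for good.** The AE form is not available for review. For serious and significant events, 7.4 provides for updated reports and further evaluations at the sponsor's request.
- **A lens-caused event has no category.** It fits Unrelated, because that category covers events with a more likely other cause. The lens-related papillary conjunctivitis in 7.1.5 is one example in a list of events, not an attribution rule.

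**Conclusion.** The point holds as a contradiction of definition. Section 7.3.2 makes a drops-only event an ADE, and possibly an ASADE or USADE, where 7.1.2 and 7.3 would not.

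Its size is modest. It touches safety attribution and regulatory classification, and the only reporting duty it can alter is the USADE report to the IRB, for an event that is drops-only, serious or significant, and unanticipated. Endpoints, margins, sample size and power are untouched. How many events would be affected cannot be derived from the documents.

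The conclusion assumes that investigators follow 7.3.2 as written and that the AE form mirrors it. If the form already records the two products separately, the wording conflict remains but the practical harm largely goes.

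**What to change.** 1. In 7.3.2 and on the AE form and expedited report form, replace the pooled rating with two Related/Unrelated ratings: (a) study solution and (b) rewetting drops.
2. State that ADE, ASADE and USADE status follows rating (a).
3. Make 7.1.2, 7.3 and 7.3.2 use the same object of assessment, and say whether an event related to the marketed Control solution is an ADE.
4. List drops-related events separately, so that they stay visible once they no longer carry the ADE label. State how an unanticipated serious event attributed only to the drops is to be notified.

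The cost is one extra field and one extra judgement per event, plus wording changes in three sections. The change is best made before events are rated, since separating them later means going back to the investigators. A separate rating for the contact lens is optional and is not needed to correct this error.

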7.4 Procedures for Reporting SAEs and Significant Non-Serious Adverse Events

An AE classified as a SAE or a Significant Non-Serious AE requires expeditious handling and reporting to the Sponsor to comply with regulatory requirements, as follows:

- The event must be reported to the Medical Monitor within 24 hours of the Investigator's awareness of the event via facsimile/email transmission on a paper SAE or Significant Non-Serious AE Report Form signed by the Investigator.

- The Medical Monitor will email a copy of the form (within 24 hours) to 

- Investigators should not wait to receive additional information to fully document the event before initially notifying the Medical Monitor of an SAE or a Significant Non-Serious AE. Additional relevant information such as hospital records and autopsy reports should be provided to the Medical Monitor as soon as they are available.
- The Investigator should take all appropriate measures to ensure the safety of the subjects: notably, he/she should follow a subject with an SAE or Significant Non-Serious AE until the event has resolved or the condition has stabilized. This may imply that follow-up will continue after the subject has left the study, and that additional evaluations may be requested by the Sponsor.
- Ensure that the subject's identity is protected and the subject's identifiers in the clinical trial are properly mentioned on the form.
- BEGIN TREATMENT OF THE AE IMMEDIATELY BY A SUITABLY LICENSED EYE CARE PROFESSIONAL.
- Continue to update the paper SAE or Significant Non-Serious AE Report Form, if applicable, each time the subject is seen during the management of the event and at resolution of the event. All updated report forms should be submitted to the Medical Monitor who will distribute the reports as stated above. Whenever possible, it is suggested that the Investigator take photographs of all applicable AEs and forward them to the Medical Monitor.
- Events requiring medical treatment will be evaluated by the Sponsor. Upon review of the medical treatment, Bausch + Lomb Clinical Operations

representatives may contact the Investigator to request further information concerning the treatment.

- Report all USADEs to the reviewing IRB within 10 working days following awareness of the USADE or according to the established reporting procedures of the IRB, whichever is shorter.
- Submit all bills, prescription receipts, and culture reports/fees related to the AE to the Bausch + Lomb Clinical Operations. Expense incurred for study related medical treatment will be paid by Bausch +Lomb Clinical Operations.

